### 11.2.1. Adverse Events Resulting in Discontinuation from Study Drug

The number and percentage of subjects with a TEAE resulting in study drug discontinuation will be presented by PT within SOC (presented in the same method as the analogous primary TEAE

table) by treatment group. More than one AE can contribute to study drug discontinuation per subject. The first line of each table will display the number and percentage of subjects with at least one TEAE leading to study drug discontinuation. This summary will be produced for both the DB period and OL period separately.

A listing of TEAEs resulting in premature study drug discontinuation will be provided, which includes subject ID, treatment period, treatment group, study day of the study drug discontinuation, and other relevant information from the AE eCRF.

### **11.2.2.** Deaths and Other Serious Adverse Events

Summary tables of treatment-emergent serious adverse events (SAEs) will be presented. The number and percentage of subjects with an SAE will be presented by PT within SOC (each sorted in alphabetical order) by treatment group. The first line of the table will display the number and percentage of subjects with at least one SAE. This table will be produced for both the DB period and the OL period separately.

Separate listings of SAEs and fatal TEAEs will also be provided. Each listing will include subject ID, treatment period, treatment group, study day of the SAE or fatal TEAE, and any additional relevant information from the AE eCRF.

### 11.2.3. Adverse Events of Acute Adrenal Insufficiency

In addition to the TEAE summaries described above, adverse events of acute adrenal insufficiency will be presented in a table by PT and treatment group. This table will be produced for the DB period and the OL period separately.

The following PT (MedDRA, version 26.0) will be used to identify AEs of acute adrenal insufficiency/adrenal crisis:

• adrenocortical insufficiency acute

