## 9.7.2. Events Requiring Glucocorticoid Stress Dosing

Subjects (and caregivers) should be educated on situations (such as illness or other events associated with significant physical stress) that require increased glucocorticoid dosing. Subjects may follow guidance provided by the investigator, their treating physician, or based on guidelines provided in Appendix A. Use of glucocorticoid stress dosing will be captured by subjects (or caregivers as appropriate) and documented in the eCRF.

The upper end of the target glucocorticoid dose (8 to 10 mg/m²/day) corresponds to the 90th percentile of normal cortisol production in healthy children and adolescents based on stable isotope methodology (Linder et al., 1990). Thus, the likelihood of causing glucocorticoid insufficiency by targeting doses in this range is considered low. Nevertheless, when reducing glucocorticoid doses (as appropriate while maintaining androgen control), investigators will evaluate subjects for any symptoms suggestive of glucocorticoid insufficiency using a standardized checklist.

Events that require glucocorticoid stress dosing, including those that require increased oral dosing, parenteral administration, emergency department evaluation, and/or hospital admission will be reviewed periodically (including by the DMC).

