### 4.6. Safety

Safety endpoints in the DB and OL periods include:

- Occurrence of treatment-emergent adverse events (TEAEs), exposure-adjusted subject incidence rate, serious adverse events (SAEs), severe TEAEs, adrenal insufficiency TEAEs, TEAEs leading to glucocorticoid stress dosing, and TEAEs leading to discontinuation from study drug
- Observed and changes from baseline in clinical laboratory test values (including hematology, clinical chemistry, thyroid stimulating hormone [TSH], free T4, plasma renin activity [PRA], and coagulation)
- Observed and changes from baseline in vital sign values
- Observed and changes from baseline in 6- or 12-lead electrocardiogram (ECG) intervals
- Observed and changes from baseline in total scores from the Brief Psychiatric Rating Scale for Children (BPRS-c)
- "Yes" responses to suicidal behavior or ideation at postbaseline assessments from the Columbia-Suicide Severity Rating Scale (C-SSRS; only for subjects ≥6 years of age)

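### SAP 4.6 lists adrenal insufficiency TEAEs as a safety endpoint, but SAP 11.2.3 retrieves one preferred term for the acute form, so no table counts subjects with any adrenal insufficiency TEAE

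*SAP*

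**What the plan says.** SAP 4.6 gives the safety endpoints for both treatment periods. The adverse event item includes "severe TEAEs, adrenal insufficiency TEAEs, TEAEs leading to glucocorticoid stress dosing, and TEAEs leading to discontinuation from study drug". Nothing there limits adrenal insufficiency to acute events or crisis.

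SAP 11.2.3 is where this endpoint becomes a table. Its heading refers to the acute form, and its text says that "adverse events of acute adrenal insufficiency will be presented in a table by PT and treatment group", separately for each period. The search rule is "The following PT (MedDRA, version 26.0) will be used to identify AEs of acute adrenal insufficiency/adrenal crisis", followed by a list with one entry, "adrenocortical insufficiency acute". No other section of the SAP defines or groups adrenal insufficiency events.

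The protocol treats glucocorticoid insufficiency as something to watch for when doses come down. Under Protocol 9.7.2 investigators will "evaluate subjects for any symptoms suggestive of glucocorticoid insufficiency using a standardized checklist", and Protocol 7.2 and 9.3.2.1 require that check before any reduction and make absence of insufficiency a condition of the target dose. Protocol 9.7.2 also states that "the likelihood of causing glucocorticoid insufficiency by targeting doses in this range is considered low".

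**The concern.** The endpoint and its table have different scopes. The endpoint covers adrenal insufficiency; the table covers adrenal crisis. This matters because glucocorticoid is lowered by design, on the same schedule in both arms, and insufficiency short of crisis is a foreseen and monitored consequence of lowering it. Someone who looks for the endpoint of SAP 4.6 will go to the table from 11.2.3. If that table shows zero or few events, the natural reading is that adrenal insufficiency was rare, when the table can only say that events coded to the acute term were rare.

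**Working it through.** There is no stated figure to reproduce, and the point depends on no power, alpha or effect-size input. The check is a comparison of text, plus two short arguments about what the planned tables can show.

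**1. Scope of endpoint against scope of table**

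| Item | SAP 4.6 | SAP 11.2.3 |
|---|---|---|
| Form named | Adrenal insufficiency, unqualified | Acute adrenal insufficiency or crisis |
| Terms for the acute form | Not listed | 1 |
| Terms for non-acute adrenal or glucocorticoid insufficiency | Not listed | 0 |
| Other SAP sections that define or group the endpoint | None | None |

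**2. Can a non-acute term arise?** Yes. Protocol 11.1 asks investigators to record the diagnosis in place of its individual signs. A diagnosis of insufficiency short of crisis, prompted for example by the symptom checklist, would be recorded as that diagnosis. Unless it coded to the acute term, 11.2.3 would not pick it up. The SAP plans no summary of the checklist itself, so adverse event coding is the planned route by which such events reach the report.

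**3. Where would it be reported?**
- General TEAE tables by SOC and preferred term, including the age and Tanner subgroups (SAP 11.2): always.
- Exposure-adjusted rates by preferred term, both periods combined (SAP 11.2.5): always.
- Drug-discontinuation and SAE displays (SAP 11.2.1 and 11.2.2): only if it led to stopping study drug or was serious.
- Stress-dosing tables (SAP 11.2.4): only if it led to stress dosing.

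So the event is not lost. Each of these displays either works term by term or selects on some other consequence of the event.

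**4. Can the endpoint be rebuilt from those rows?** Not in general. Suppose the insufficiency terms in one arm have subject counts n1, n2, ..., nk. One subject may appear under several terms, so the number of subjects with any such TEAE is bounded only by

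max(n1, ..., nk) ≤ N_any ≤ n1 + n2 + ... + nk.

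The two ends agree only if at most one term has events. With more than one, the count for SAP 4.6 needs subject-level data.

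**5. What would a zero in 11.2.3 mean?** SAP 3.3 plans 54 crinecerfont subjects. With 0 events in 54, the one-sided 95% upper limit is 1 − 0.05^(1/54) = 0.054, or 5.4%. That limit applies to the acute term alone. It places no limit on the rate of the broader endpoint.

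**The case against.** The best defence is that 11.2.3 is consistent in heading, text and term, and that a focus on crisis is sensible in this disease. Every subject has cortisol deficiency at entry, and Protocol 11.1 does not count a persistent pre-existing condition as an adverse event unless it unexpectedly progresses or worsens. On this view SAP 4.6 is shorthand for the acute table. The section is also presented as a supplement to the general TEAE tables, where in a trial of about 81 subjects any insufficiency term would have its own visible row by arm. Safety is descriptive (SAP 11), so no test depends on the table.

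Much of this stands. The other displays do report non-acute events by arm, and an acute table is worth keeping. But worsening under dose reduction would be an adverse event under Protocol 11.1, and the SAP nowhere says that 4.6 means acute only. A table with one preferred term also largely repeats a row of the general table, whereas an endpoint table is useful because it groups related terms.

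Three stronger readings are tempting, and the documents do not support them. A reader might infer that non-acute events go unreported; item 3 of the working shows that they do not. A reader might call insufficiency the expected harm of the titration; Protocol 9.7.2 calls its likelihood low, so foreseen and monitored is as far as the text goes. A reader might conclude that crinecerfont would look safer than it is, because the titration guide (Protocol Tables 3 and 9) ties larger reductions to larger falls in androstenedione. That is an inference: both arms share the same target dose and the same symptom check, and no document gives event rates by arm.

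**Conclusion.** The mismatch is real and its consequence is limited. The endpoint named in SAP 4.6 has no table that delivers it, and 11.2.3 supports statements about the acute form only. The gap is one grouped count per arm and period, not missing data. The size and direction of any undercount are unknown: an estimate would need both an event rate and the share of events coded to the acute term, and the documents give neither. The conclusion rests on reading SAP 4.6 as written, without an implied restriction to acute events, and on MedDRA 26.0 offering at least one relevant non-acute term, which the documents do not list. It is worth correcting because the correction is cheap and the protocol's view that the risk is low needs a count to support it.

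**What to change.** Before unblinding, add to SAP 11.2.3 a fixed list of MedDRA 26.0 preferred terms for adrenal, adrenocortical or glucocorticoid insufficiency. Report the number and percentage of subjects with any such TEAE by treatment group, separately for the double-blind and open-label periods, and keep the acute term as a sub-row. Show any glucocorticoid-withdrawal terms on a separate line, because they go beyond the wording of 4.6 and should not enter the endpoint count. If the sponsor intended the acute form only, the minimum change is to say so in 4.6; that aligns the label with the table but leaves non-acute events without a grouped count.

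The cost is a term list, a short SAP edit and a little programming, with no new data and no change in trial conduct. The reported count may rise. Timing matters: under SAP 6.1, an analysis defined after the Week 28 database lock is post hoc.

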### 11.2.4. Adverse Events Leading to Glucocorticoid Stress Dosing

The number and percentage of subjects with a TEAE leading to glucocorticoid stress dosing will be presented by PT within SOC (presented in the same method as the analogous primary TEAE table) by treatment group. The first line of each table will display the number and percentage of subjects with at least one TEAE leading to glucocorticoid stress dosing. This summary will be produced for both the DB period and OL period separately.

An overall summary table will be provided that summarizes the maximum severity of glucocorticoid stress dosing based on the following categories (in order of least to most severe):

- Oral dosing (alone, without parenteral dosing/ER visit/SAE)
- Parenteral dosing (without ER visit/SAE)
- ER visit without SAE (requiring glucocorticoid stress dosing)
- SAE (requiring glucocorticoid stress dosing)

Each subject will be counted once by their maximum severity of illness requiring glucocorticoid stress dosing. This table will be produced for the DB period and the OL period separately.

#### 11.2.5. Exposure-Adjusted Subject Incidence Rate

Exposure-adjusted subject incidence rate will be defined as the number of unique subjects experiencing the TEAE one or more times (numerator) divided by the sum of the time at risk for the first TEAE across all subjects (denominator). For subjects experiencing the TEAE, the time at risk (exposure time) is the time from the first dose to the date of the first occurrence of the TEAE. For subjects not experiencing the TEAE, exposure time is the time from the first dose to the last dose + 28 days (or data cutoff). Note that exposure time will vary across subjects for the same TEAE. The exposure-adjusted subject incidence rate in the crinecerfont and placebo groups, over the DB and OL periods combined, will be summarized by descending preferred term in the crinecerfont group.

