## **1. INTRODUCTION**

The purpose of this statistical analysis plan (SAP) is to describe the planned analyses and data displays that will be prepared to summarize the data from the double-blind, placebo-controlled treatment period (Day 1 to Week 28; "DB period") and open-label treatment period (Week 28 to Week 52; "OL period") of the Phase 3 Study NBI-74788-CAH2006. Summaries of data from the open-label extension (OLE) for continued access to crinecerfont (starting after Week 52) will be described in a separate SAP.

This SAP was developed in accordance with International Council for Harmonization (ICH) E9 guidance. Data analyses described in this SAP will occur at 2 milestones in the study: after all subjects have had the opportunity to complete Week 28 and after all subjects have had the opportunity to complete Week 28 and after all subjects have had the opportunity to complete Week 52. The first analysis will include the final analysis of data through Week 28 and an analysis of all available safety and efficacy data up to Week 52. The second analysis will be the final analysis of data through Week 52. Decisions regarding each set of analyses will be made prior to the corresponding database lock and treatment unblinding and will be documented. Changes to the planned analyses described in this SAP will be statistically justified and described in the clinical study report (CSR). Further information related to study design and methodology can be found in the study protocol.

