## 11.2. Adverse Events

A treatment-emergent adverse event (TEAE) is an AE not present prior to the initiation of study drug dosing, or is an already present event that worsens either in intensity or frequency following the initiation of study drug dosing with an onset on or before the last dose of study drug + 28 days (to account for the study drug washout period).

TEAEs will be further defined for the two treatment periods. For the DB period, Investigators will be asked to respond "Yes" or "No" on the eCRF as to whether the AE started after the subject took the first dose of study drug. An AE with a response of "Yes" and that occurs on or before the last dose of study drug in the DB period will be classified as a TEAE for the DB period. If the subject's last dose on study occurs in the DB period, then any AE occurring prior to or on the last dose of study drug in the DB period + 28 days will be considered a TEAE. If the investigator's response is missing, then the treatment emergent status will be derived based on the AE onset date relative to the date of the subject's first dose of study drug in the DB period or first dose of study drug in the OL period. If the AE onset date is unknown, it will be assumed that the AE is a TEAE and will be reported in the DB period TEAE summaries.

For the OL period, TEAEs will be defined as AEs starting after the first dose of study drug in the OL period and prior to the last dose of study drug in the OL period. If the subject's last dose on study occurs in the OL period, then any AE occurring prior to or on the last dose of study drug in the OL period + 28 days will be considered a TEAE.

TEAEs that are ongoing at the time of a datacut will be summarized once according to the treatment period in which the TEAE started.

Adverse events with an onset date after the last dose of study drug + 28 days will not be considered treatment emergent (non-TEAEs).

The following TEAE summaries will be produced for the DB period (Day 1 up to Week 28) and for the 6-month OL period (Week 28 to Week 52) separately:

- TEAEs categorized by MedDRA system organ class (SOC) and/or preferred term (PT) will be summarized in frequency tables. The frequency tables will include the number and percentage of unique subjects experiencing each event one or more times by treatment group.

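### SAP 11.2.5 can count up to 28 days at risk after the last open-label dose in which SAP 11.2 counts no event, lowering the exposure-adjusted rates by at most 7.1%

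*SAP*

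**What the plan says.** SAP Section 11.2.5 divides the number of subjects with a treatment-emergent adverse event (TEAE) by the summed time at risk for the first such event. For a child with the event, "the time at risk (exposure time) is the time from the first dose to the date of the first occurrence of the TEAE". A different rule covers a child without it: "exposure time is the time from the first dose to the last dose + 28 days (or data cutoff"). The rate is reported for the two groups "over the DB and OL periods combined", that is, the double-blind (DB) and open-label (OL) periods. The section defines neither the last dose nor the data cutoff.

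SAP Section 11.2 decides which events count. It opens with a general definition, an event "with an onset on or before the last dose of study drug + 28 days", and gives drug washout as the reason for the 28 days. It then narrows this by period. The OL rule covers only "AEs starting after the first dose of study drug in the OL period and prior to the last dose of study drug" of that same period, and the 28 days are added only under a condition: "If the subject's last dose on study occurs in the OL period". SAP Section 1 says that summaries of OLE data "will be described in a separate SAP".

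**The concern.** An incidence rate needs one observation window, in which a day counts as at risk only if an event on that day would be counted. Here the two sections end the window differently for a child who goes on to the OLE. Section 11.2 makes the tail conditional, which is sensible: such a child keeps dosing, so there is no washout, and Protocol Section 7.5 waives the post-treatment visit. Section 11.2.5 adds the tail without that condition. Any resulting error makes a safety rate look lower than it is, and this is the SAP's only exposure-standardised safety rate.

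**Working it through.** The plan states no figure for this rate, so there is nothing to reproduce. The check sets the two rules side by side and then sizes the gap.

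**Inputs**
- Planned DB plus OL time, T: 28 + 24 = 52 weeks = 364 days (Protocol Section 9.9; SAP Table 4 also targets Week 52 at day 364).
- Tail: 28 days (SAP Section 11.2.5).
- Share entering the OLE, s: not in the documents; assumed 50% to 100%.
- Proportion with the event by day 364, p: not in the documents; assumed near 0 to 80%, with constant hazard, full 52-week follow-up, and OLE entry unrelated to the event.

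**Step 1: where each window ends for a child without the event**

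| Child | Events counted to (11.2) | Time counted to (11.2.5) | Excess |
|---|---|---|---|
| Last dose on study is in the OL period | last dose + 28 days | last dose + 28 days | 0 |
| Enters the OLE, later calendar cutoff | last OL dose | last OL dose + 28 days | up to 28 days |
| Enters the OLE, cutoff is the child's end of Week 52 data | last OL dose | end of Week 52 data | 0 |

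A child with the event stops contributing at its first occurrence and adds no excess.

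**Step 2: formula for the middle row, with the cutoff at least 28 days after the last OL dose**
- Mean matched time at risk per child: PT = p/λ, with λ = −ln(1 − p)/364.
- Mean excess per child: E = s × (1 − p) × 28.
- Relative understatement of the rate: E/(PT + E). As p approaches 0, PT approaches 364.

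**Step 3: results**

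| p | s | PT (days) | E (days) | Understatement |
|---|---|---|---|---|
| near 0 | 100% | 364 | 28 | 28/392 = 7.1% |
| 10% | 100% | 345.5 | 25.2 | 25.2/370.7 = 6.8% |
| 50% | 100% | 262.6 | 14.0 | 14.0/276.6 = 5.1% |
| 80% | 100% | 180.9 | 5.6 | 5.6/186.5 = 3.0% |
| near 0 | 50% | 364 | 14 | 14/378 = 3.7% |
| 80% | 50% | 180.9 | 2.8 | 2.8/183.7 = 1.5% |

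**Step 4: worked example.** Take the 54 crinecerfont subjects of SAP Section 3.3 and assume 5 have the event, at mean day 182, and all 49 others enter the OLE.
- Matched windows: 5 × 182 + 49 × 364 = 18,746 days; 5/18,746 × 365.25 × 100 = 9.74 per 100 subject-years.
- As written: 5 × 182 + 49 × 392 = 20,118 days; 9.08 per 100 subject-years.
- Difference: 1 − 18,746/20,118 = 6.8%.

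**The case against.** There are three substantial replies.

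- **The cutoff may remove the gap.** SAP Section 5.2 limits the final analysis to data up to Week 52, and SAP Table 4 closes the Week 52 visit window at the first OLE dose. If the cutoff in Section 11.2.5 means the same, the understatement is 0%. This stands as a possible reading, but the SAP does not state it. Section 11.2 refers to events still ongoing at a datacut, which reads more like a calendar date. A calendar date more than 28 days after a child's last OL dose removes nothing.
- **The general TEAE definition also runs to last dose + 28 days.** On this view the period-specific windows serve the separate DB and OL tables, and the combined table uses the general one. But for a child dosing in the OLE, the general window would continue through OLE treatment, which Section 11.2.5 leaves out of its stated periods and Section 1 assigns elsewhere. It does not reconcile the two sections.
- **The effect is small.** SAP Section 11 plans no hypothesis tests of safety data, and counts and percentages are tabulated separately. In the example, the exact Poisson 95% interval around 9.74 is about 3.2 to 22.7, far wider than the shift to 9.08. This stands and sets the severity.

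The case for a mismatch can also be pushed too far. A reader might infer that children who withdraw or are lost add many unobserved days. Protocol Sections 9.11.1 and 9.11.2 keep children who stop study drug in follow-up to Week 52 and ask those who withdraw to return about 4 weeks after the last dose unless consent is withdrawn, so only a small remainder is unobserved.

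**Conclusion.** The two windows do not match for event-free OLE entrants under the natural reading: last dose is the last OL dose and the cutoff is a later calendar date. The group exposure-adjusted rates over DB plus OL are then too low by at most 7.1%, and by 1.5% to 7.1% across the assumed ranges of incidence and OLE uptake. If the cutoff is each child's end of Week 52 data, the error is zero. The point is minor, because the table is descriptive.

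Three stronger conclusions are not supported:
- A reader might take last dose to mean the last dose on study, so that OLE time accrues up to the cutoff and the error grows well beyond 28 days. That conflicts with the DB plus OL scope of the rate and with the separate SAP for the OLE.
- A reader might infer that the rate is understated for every child who enters the OLE. The rate is a group figure, and only event-free entrants add excess time.
- A reader might infer a bias in the comparison between groups. Both have the same planned 364 days, and the documents give no reason to expect different OLE uptake. If incidence were 10% in one group and 50% in the other, with all entering the OLE, the rate ratio would be multiplied by (1 − 0.068)/(1 − 0.051) = 0.98, a smaller change than in either absolute rate.

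**What to change.** In SAP Section 11.2.5, end time at risk for an event-free subject where Section 11.2 ends event capture:
- at the last OL dose for a subject who enters the OLE;
- otherwise at the earliest of last dose + 28 days, end-of-study date and data cutoff.

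State that last dose means the last dose in the DB or OL period, and define the data cutoff. The end-of-study limit also removes unobserved days for children who withdraw or are lost.

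The cost is about one SAP sentence and a small programming change, with no new data. Under the later-cutoff reading, the reported rates become slightly less favourable.

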## 5. DATA ANALYSES

## 5.1. Week 28 (DB Period) Final Analysis

The final unblinded analysis of the double-blind, placebo-controlled period will be conducted once all subjects have had the opportunity to complete the Week 28 visit. Data through Week 28, including the primary, key secondary, secondary, and exploratory endpoints occurring on or before Week 28, will be analyzed. At this time, an analysis of all available safety and efficacy data through Week 52 will also be performed. Following this analysis, the subject, investigator, all study center personnel, and Sponsor personnel with direct contact with the site will continue to be blinded to the subject's blinded treatment assignment. All planned analyses for the final Week 28 analysis are included in this SAP.

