# 6. GENERAL CONSIDERATIONS FOR DATA ANALYSES AND HANDLING

### 6.1. General Statistical Procedures

All analyses described in this plan are considered a priori analyses in that they have been defined prior to locking the study database for the Week 28 analysis. Analyses defined subsequent to locking the database will be considered post hoc analyses and will be applied as exploratory methodology. Any post hoc analyses will be statistically justified and described as appropriate in the CSR. Statistical analysis will be conducted, and all tables, figures, and listings generated using SAS® software (version 9.4 or later), unless stated otherwise.

Unless otherwise noted, data from the double-blind, placebo-controlled period (Day 1 to Week 28; "DB period") will be summarized by randomized treatment group, defined as crinecerfont or placebo (DB treatment group). Data from the open-label period (Week 28 to Week 52; "OL period") will be summarized by OL treatment group, defined as placebo/crinecerfont or crinecerfont/crinecerfont to describe the subject's randomized treatment assignment and their OL treatment, as well as all subjects combined. Note that while crinecerfont (and matching placebo) dose levels (25 mg bid via oral solution for subjects 10 to <20 kg, 50 mg bid via oral solution for subjects 20 to <55 kg, or 100 mg bid via oral capsules for subjects  $\geq$ 55 kg) are assigned based on weight at Day 1 and again at Week 28, summaries of the DB and OL period data will not be broken out by dose level unless otherwise specified.

Descriptive and inferential statistical methods will be used to evaluate and summarize the data from this study. The term "descriptive statistics" refers to the number of subjects (n), mean, median, standard deviation (SD) or standard error (SE), minimum, and maximum for continuous variables. Ordinal categorical data will be summarized using median, minimum and maximum values. Number and percentage of subjects will be summarized for categorical variables. The term "inferential statistics" refers to hypothesis tests that will be performed to assess differences between the treatment group and the control group. All hypothesis tests will be tests of the null hypothesis of no difference between the groups being compared versus the two-sided alternative hypothesis that there is a difference. The level of significance (type I error) for declaring statistical significance will be 0.05.

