# 11.1. Study Drug Dosing and Compliance

The duration of exposure to crinecerfont will be calculated as: last dose date – first dose date +1.

Duration of exposure to crinecerfont will be summarized with descriptive statistics over the DB and OL periods (ie, table will include cumulative exposure from both treatment periods). The number and percentage of subjects with the following exposure categories will also be presented:

- > 0 to < 4 weeks
- $\geq$  4 weeks to < 16 weeks
- $\geq 16$  weeks to < 28 weeks
- $\geq 28$  weeks to < 40 weeks
- $\geq$  40 weeks to < 52 weeks
- $\geq 52$  weeks

At each visit where study drug is dispensed, the site will enter the kit number(s) dispensed and returned as well as the total number of capsules dispensed and returned for the kits combined. The subject's compliance will be calculated at each visit (when kits are returned) as the total number of capsules dispensed – total capsules returned divided by the expected number of capsules taken by the subject during the visit interval. For subjects receiving the oral solution, compliance will be determined based on the weight of the dispensed and returned study drug. The number and percentage of subjects in each treatment group who are dosing compliant (defined as < 80%,  $\ge$  80% to  $\le$  120%, > 120%) will be presented for each postbaseline visit when study drug is returned. Compliance will be summarized separately for the DB and OL periods.

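### SAP 11.2.5 pools the double-blind and open-label periods into one exposure-adjusted rate for the crinecerfont and placebo groups, with no rule for the placebo group's switch to crinecerfont at Week 28

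*SAP*

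**What the plan says.** SAP 11.2.5 defines a subject incidence rate: the number of subjects with a given treatment-emergent event, divided by the summed time at risk for the first such event. For a child with the event, time runs from first dose to first occurrence. For a child without it, "exposure time is the time from the first dose to the last dose + 28 days (or data cutoff"). The result is to be shown for "The exposure-adjusted subject incidence rate in the crinecerfont and placebo groups, over the DB and OL periods combined". The section does not define the two groups, does not say which study drug's first and last dose is meant, and does not mention Week 28.

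Four other places bear on it:

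- **SAP 6.1** groups double-blind data by randomized treatment, "defined as crinecerfont or placebo (DB treatment group"). Open-label data "will be summarized by OL treatment group, defined as placebo/crinecerfont or crinecerfont/crinecerfont". No label is given for a table covering both periods.
- **SAP 11** makes separate periods with period-specific groups the default unless otherwise noted. Section 11.2.5 departs from the first part of that default without replacing the second.
- **SAP 11.1** summarizes exposure to crinecerfont over both periods: "table will include cumulative exposure from both treatment periods".
- **SAP 11.2** assigns events to periods by onset, open-label events being "AEs starting after the first dose of study drug in the OL period" and before the end of that period's dosing. It gives no matching split of time at risk.

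Protocol 7.3 and SAP 3 put every child on crinecerfont from Week 28 to Week 52.

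**The concern.** A column headed placebo in a safety table will be read as a control rate. If children randomized to placebo keep that label after Week 28, events and time on open-label crinecerfont enter the placebo numerator and denominator. A sustained effect of the drug then raises both columns, and their ratio moves toward 1.

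SAP 4.6 lists this rate among the safety endpoints, and it is the only exposure-adjusted rate in the plan. Mixing can also enter the first unblinded report, because SAP 5.1 adds to the Week 28 analysis: "At this time, an analysis of all available safety and efficacy data through Week 52 will also be performed". Two programmers could both follow 11.2.5 and produce different tables.

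**Working it through.** **Inputs from the documents.** 28 double-blind weeks, then 24 open-label weeks with all children on crinecerfont (SAP 3); 54 children on crinecerfont and 27 on placebo (SAP 3.3); a 28-day tail after last dose (SAP 11.2.5).

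**Check on the durations.** The plan gives no figure for the share of placebo-group time spent on crinecerfont. Its nearest total is the approximately 60 weeks of participation in Protocol 9.9, which reproduces: 4 + 28 + 24 + 4 = 60.

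**Share of placebo-group time, randomized labels.**

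- Planned dosing: 27 × 28 = 756 child-weeks on placebo and 27 × 24 = 648 on crinecerfont, in total 1,404. Share: 648/1,404 = 24/52 = 46.2%.
- With the 4-week tail, for a child without the event: 24/56 = 42.9% counting dosing weeks only, and 28/56 = 50.0% counting all time after the switch.

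**The two readings side by side.**

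| Reading | Placebo child-weeks | Crinecerfont child-weeks |
|---|---|---|
| Randomized labels | 1,404 | 54 × 52 = 2,808 |
| As treated, split at first open-label dose | 756 | 2,808 + 648 = 3,456 |

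The placebo denominators differ by a factor of 1,404/756 = 1.86.

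**Effect on a rate ratio.** The documents give no event rates, so this part is assumed: constant hazards, a placebo rate λ of 0.05 to 1.0 per year (52-week year), a crinecerfont rate of λR, no dropout, and the crinecerfont hazard in the tail. Let T be the time after the switch (24 weeks, or 28 with the tail) and S = exp(−28λ), with λ per week.

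- Expected share of placebo-group children with the event: 1 − S·exp(−λRT)
- Expected time at risk: (1 − S)/λ + S·(1 − exp(−λRT))/(λR)
- Displayed placebo rate: the first divided by the second
- Displayed ratio: λR divided by that rate

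Example with λ = 0.1 per year, R = 2, T = 24: S = exp(−0.1 × 28/52) = 0.9476. Events: 0.1360 per child. Time: 27.26 + 21.72 = 48.98 weeks. Displayed placebo rate: 0.1360/48.98 × 52 = 0.1443 per year, against a true 0.1. Displayed ratio: 0.2/0.1443 = 1.386.

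| Placebo rate per year | True ratio 2.0, no tail | True ratio 2.0, 4-week tail |
|---|---|---|
| 0.05 | 1.377 | 1.342 |
| 0.1 | 1.386 | 1.351 |
| 0.3 | 1.420 | 1.388 |
| 0.6 | 1.473 | 1.445 |
| 1.0 | 1.542 | 1.520 |

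A hand check for rare events agrees: without the tail the placebo rate is inflated by (28 + 24 × 2)/52 = 1.46, and 2.0/1.46 = 1.37; with it, by (28 + 28 × 2)/56 = 1.50, and 2.0/1.50 = 1.33.

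Over the same grid, a true ratio of 1.5 shows as 1.20 to 1.29, and 3.0 as 1.52 to 1.98. At the Week 28 data cutoff less open-label time has accrued. If every child had 6 open-label weeks, 2.0 would show as 1.70 to 1.78; with 12 weeks, as 1.55 to 1.66. Those two accrual times are also assumptions.

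**The case against.** The strongest reply is that the table may be meant as treated. SAP 11.1 pools crinecerfont exposure over both periods, SAP 6.1 confines the randomized labels to double-blind data, and adjusting for exposure is most useful where crinecerfont time (up to 52 weeks) exceeds placebo time (28). Split at the first open-label dose, that table has no dilution. This stands as a plausible intention. It does not rescue the text, which gives no instruction to stop a placebo child's clock and start another. The labels match the randomized groups of SAP 6.1, so a literal reader reaches the mixed version. SAP 10.6, which also spans both periods, does state its grouping.

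The second reply concerns weight, and it stands too. SAP 11 plans no hypothesis test on safety data, and the main adverse-event tables are produced separately by period. Precision is also low. At a placebo rate of 0.1 per year, about 27 × (1 − exp(−0.1 × 28/52)) = 1.4 placebo children would have the event in the double-blind period, against 54 × (1 − exp(−0.2 × 28/52)) = 5.5 on crinecerfont if the true ratio is 2. The approximate 95% interval, 2 × exp(±1.96 × √(1/1.4 + 1/5.5)), is 0.3 to 12.7. A shift from 2.0 to 1.4 lies well inside that. It is nevertheless a shift in one direction, created by the definition and removable at little cost.

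A reader might go further in two ways that the documents do not support. One is to say that the 28-day tail makes placebo time overlap open-label time even in an as-treated table. SAP 11.2, the parent section, allows the double-blind tail only where the subject's "last dose on study occurs in the DB period, then any AE occurring prior to or on the last dose" plus 28 days counts. The other is to say that the double-blind tables fail for common events. That sets a ratio of proportions against a ratio of rates, which is a difference of scale; planned double-blind follow-up is 28 weeks in both arms.

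**Conclusion.** The concern holds as a defect in one definition. Read literally, SAP 11.2.5 produces a placebo rate that is partly a crinecerfont rate, and neither SAP 6.1, 11 nor 11.2 repairs it. The 46% follows from the planned durations alone. It is a share of planned dosing time, not an upper bound and not a forecast: it becomes 43% to 50% of time at risk with the tail, and it falls for common events because the clock stops at the first event. The displayed ratio of about 1.3 to 1.5 for a true 2.0 depends on randomized labels, constant hazards, full follow-up to Week 52 and assumed placebo rates of 0.05 to 1.0 per year.

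It would be tempting to infer that the trial's safety comparison is compromised or that harm would go unseen. The documents do not support that. Protocol 13.6.2 and SAP 11.2 keep a separate double-blind tabulation by randomized group, which is unmixed, and this table is descriptive. Nor do they show that the sponsor intends the mixed version; they show only that the text permits it and gives no rule for the alternative. The change should be made before the table is programmed.

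**What to change.** In SAP 11.2.5, replace the single combined display with two:

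1. **Double-blind rates by randomized group.** In both arms, events and time end at the first open-label dose, or at the last double-blind dose plus 28 days for a child who never enters the open-label period.
2. **An all-crinecerfont rate.** Events and time are counted from each child's first crinecerfont dose: Day 1 for those randomized to crinecerfont, the first open-label dose for those randomized to placebo.

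If a combined display by randomized arm is kept, for example to show effects that appear only after longer treatment, label its columns placebo/crinecerfont and crinecerfont/crinecerfont, as SAP 6.1 already does for open-label data.

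Cost: SAP wording, some programming and one more table. No new data are needed.
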